### **3.3.5. Safety Follow-up Period**

The safety follow-up period will comprise 40 calendar days after the last administration of the IP.

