#### **6.4.4. Visits 11, 14, 17, 20, and Early Study Discontinuation or End of Study Visit**

At the annual visits (Weeks 52, 104, 156, and 208) or early study discontinuation or end of study visit, the following procedures and assessments should be completed. Except for the EDC or EOS visits, all of the procedures should be completed before the self-administration of IP. When the criteria for stopping the trial outlined in [Section 3](#) have been met, the study sites will be contacted by the study team and told to instruct their subjects to discontinue taking IP. EOS visits should be scheduled as soon as possible after that announcement. The EOS visit should be scheduled to occur no sooner than 14 days after the last dose of IP was administered. The safety follow-up period is 40 days after the last dose of IP was administered for subjects taking IP. If their EOS visit has occurred less than 40 days after the last dose of IP was administered, subjects will receive a telephone call to determine if any serious adverse events have taken place. All EOS procedures should be done for all randomized subjects when the study is completed whether or not the subject is taking double-blind IP.

All EDC procedures should be done upon the permanent early discontinuation of double-blind IP. Subjects should continue to have visits with study personnel according to the study schedule until study completion. If a subject has not fully withdrawn consent for further contact with the study site, the subject should be encouraged to remain in contact with the investigator, either by attending study visits or via phone visit, throughout the remainder of the study. The study management team will provide to the study site, an EDC retention hotline, and a study retention toolkit, to define potential levels of the subject's continued participation in the study. Every effort must be made to retain subjects in the study, even if they are no longer taking IP.

- **Laboratory test review:** There should be a review of results from laboratory values of the previous visit.
- **Vital signs:** Temperature, PR, and BP will be measured and recorded in the CRF as described in [Section 7.2.3.1](#).

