ADA (nAb) positive subjects will further be classified according to the type of ADA (nAb) response (treatment induced/treatment boosted/indeterminate):

A subject will be considered as having treatment induced ADAs (nAbs) if:

- The subject is ADA (nAb) negative at baseline with at least 1 ADA (nAb) positive post-dose measurement, or
- The subject's baseline ADA (nAb) sample is missing with an ADA (nAb) negative post-dose measurement followed by at least 1 ADA (nAb) positive post-dose measurement.

A subject will be considered as having indeterminate ADAs (nAbs) if:

- The subject's baseline ADA (nAb) sample is missing with at least 1 ADA (nAb) positive post-dose measurement that was not preceded by an ADA (nAb) negative post-dose sample.

A subject will be considered as having treatment boosted ADAs (nAbs) if:

- The subject's baseline sample was ADA (nAb) positive with an increase in ADA (nAb) titer of >1.58 unit increase in titer from a positive baseline titer in at least 1 post-dose measurement.

Timing of ADA (nAb) Positive Measurement:

ADA (nAb) positive subjects will also be classified according to the timing of the ADA (nAb) positive measurement with respect to last dose of bococizumab (on treatment/off treatment):

A subject will be considered as having on-treatment ADAs (nAbs) if:

- The subject has any ADA (nAb) detected within ≤ 14 days after last dose.

A subject will be considered as having off-treatment ADAs (nAbs) if:

- The subject has their first ADA (nAb) detected >14 days after last dose.

Duration of ADA (nAb) Response:

ADA (nAb) positive subjects will also be classified according to the duration of ADA (nAb) response (indeterminate/persistent/transient) if the date of the first post-baseline measurement to the date of the last post-baseline measurement is at least 16 weeks:

A subject will be considered as having indeterminate duration of ADAs (nAbs) if:

- The subject has a positive ADA (or nAb) detected at the last post-baseline time point only

A subject will be considered as having persistent duration of ADA (nAb) if:

- The subject has positive ADA (or nAb) detected at all post-baseline samples assayed during any period of at least 16 weeks

A subject will be considered as having transient duration of ADA (nAb) if:

- The subject has been classified as neither persistent nor indeterminate

ADA (nAb) titer response:

Subjects will also be classified according to their maximum ADA (nAb) titer as

- ADA (nAb) negative,

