- 11 ADA/PK/PCSK9 sampling: Anti-drug antibody (ADA), bococizumab drug, and PCSK9 blood samples should be collected in all subjects, at the baseline and designated visits as described in Protocol Section 6 For Visit 3, only a PCSK9 sample is needed. No PK or ADA sample is needed at Visit 3. After randomization, if lipid sampling has been postponed to an unscheduled visit, the corresponding ADA/PK/PCSK9 samples should be postponed as well, and collected at the same time as the rescheduled lipid sample collection. ADA, PK, and PCSK9 samples will be collected at EDC/EOS visits.
- 12 Hematology: Complete blood count (CBC) with white blood cell (WBC) and red blood cell (RBC) counts, hemoglobin, hematocrit, WBC differential and platelet count. All hematology studies are to be performed by central laboratory.
- 13 Urinalysis: Dipstick urinalysis will be performed by study site, locally. Details describing what is evaluated in the urinalysis are described in Protocol Section 7.2.1.2, Table 2. At the screening visit a central lab urine albumin/creatinine ratio assessment may be evaluated, in subjects who have had a cardiovascular event more than 5 years prior to screening and in subjects without a prior qualifying cardiovascular event.

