- 28 Early discontinuation (EDC) procedures should be done upon the permanent early discontinuation of double-blind IP. Study sites must contact the study retention team, or delegate, or EDC retention hotline, by telephone or email, for all potential or actual EDC subjects. Subjects should continue to have visits (either in person or via phone visit) with study personnel according to the study schedule until study completion. Subjects who continue in the study, after EDC, should also complete EOS procedures, at the time of study completion.
- 29 The EOS will be announced to study sites, when the Sponsor estimates that criteria for stopping the study in Protocol Section 3 have been satisfied. EOS visits should be scheduled as soon as possible after that announcement. The EOS visit should occur no sooner than 14 days after the last dose of IP was administered for subjects taking IP. The safety follow-up period is 40 days after the last dose of IP was administered. If their EOS visit has occurred less than 40 days after the last dose of IP was administered, subjects should be contacted by telephone to determine if any serious adverse events have occurred. All EOS procedures should be done for all randomized subjects when the study is completed, including those who had an EDC visit, if they continued in the study, ie, EOS procedures should be completed, whether or not the subject is taking double-blind IP.

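### The 14-day cut-off labels almost any antibody first seen at the end-of-study sample as off-treatment, even if it formed during dosing

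*SAP*

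**What the plan says.** SAP 8.2.4.1.1, under the timing of positive measurements, defines two classes for ADA- and nAb-positive subjects.

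- On-treatment: "The subject has any ADA (nAb) detected within ≤ 14 days after last dose".
- Off-treatment: "The subject has their first ADA (nAb) detected >14 days after last dose".

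The visit rules that determine when the last sample can be drawn are elsewhere.

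- SAP Appendix 2, footnote 29: "The EOS visit should occur no sooner than 14 days after the last dose of IP was administered for subjects taking IP". Protocol 6.4.4 sets the same minimum.
- No latest day is given. EOS has no visit window, and the only instruction is "EOS visits should be scheduled as soon as possible after that announcement".
- On sampling, SAP Appendix 2 states: "ADA, PK, and PCSK9 samples will be collected at EDC/EOS visits".
- Protocol 6.4.2 to 6.4.4 places the scheduled post-baseline ADA samples at Visits 6, 8, 10, 12, 14, 17 and 20, which are Weeks 4, 14, 40, 70, 104, 156 and 208.

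SAP 8.2.3 and 8.2.4.2 report numbers and percentages of positive subjects by this on/off-treatment class. Neither has a class for a first positive whose onset cannot be placed before or after the last dose.

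**The concern.** The label depends on the date of detection, while the first opportunity to detect is fixed by the visit schedule. For a subject who dosed until the program stopped, the next ADA sample after the last scheduled one is normally EOS. Suppose a subject is negative at Week 40, seroconverts at Week 50 while injecting every two weeks, and takes the last dose at Week 60. The first positive comes at EOS, so the subject is counted as having off-treatment antibodies unless EOS fell on exactly day 14.

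The error runs in one direction. Antibodies that formed on drug can move into the off-treatment row, but the rule has no offsetting movement the other way. A reader of the table would see too little immunogenicity during treatment and could conclude that antibodies tend to appear after withdrawal. Immunogenicity is a stated safety objective (SAP 2.2), and Protocol 1.2.3 reports 42.5% ADA positivity (201/473) in earlier studies, so the table is likely to hold many subjects.

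**Working it through.** The plan states no figure for this split, so there is nothing to reproduce. The check has three parts.

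**1. Overlap of permitted EOS days with on-treatment days.** EOS is permitted on day 14 or later; on-treatment means day 14 or earlier. The two sets share one day, day 14. If EOS falls on days 14 to H, the share of permitted days on which a first positive is called off-treatment is (H − 14)/(H − 13). H is an assumption, because the documents give no upper limit.

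| H | Off-treatment days / permitted days | Share |
|---|---|---|
| 21 | 7/8 | 88% |
| 28 | 14/15 | 93% |
| 40 | 26/27 | 96% |
| 60 | 46/47 | 98% |

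These are shares of calendar days, not of subjects.

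**2. Gaps between scheduled ADA samples.** From Weeks 0, 4, 14, 40, 70, 104, 156 and 208, the gaps are 4, 10, 26, 30, 34, 52 and 52 weeks. After Week 14 no gap is shorter than 26 weeks.

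**3. Dosing time not covered by a scheduled sample.** For a subject whose last dose is in week T, the share of dosing time after the last scheduled sample is (T − last ADA week at or before T)/T.

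| T | Calculation | Share |
|---|---|---|
| 39 | (39 − 14)/39 | 64% |
| 40 | (40 − 40)/40 | 0% |
| 52 | (52 − 40)/52 | 23% |
| 60 | (60 − 40)/60 | 33% |
| 69 | (69 − 40)/69 | 42% |
| 71 | (71 − 70)/71 | 1% |
| 103 | (103 − 70)/103 | 32% |

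For T from 14 to 208, the range is 0% to 64%, with the maximum at Week 39. The simple average over T = 5 to 104 is 29%.

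**Sensitivity to when antibodies form.** If seroconversion were uniform over dosing time, these shares would also be the shares of seroconversions first seen at EOS. If onset is instead exponential with mean m weeks and occurs before T, the share is (e^(−L/m) − e^(−T/m))/(1 − e^(−T/m)), where L is the last ADA week at or before T. With m = 8 or 12 (illustrative assumptions), the average over T = 5 to 104 falls from 29% to 7% or 10%, and the Week 60 value falls from 33% to 0.6% or 2.9%.

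**The case against.** **The label concerns measurement, not onset.** The heading refers to the positive measurement, and SAP 8.2.4.2 speaks of when the result occurred relative to dosing. On that reading, a first positive on day 20 is correctly filed. This limits the harm but does not remove it: the class assigned is having off-treatment antibodies, and the table gives a reader no warning that such antibodies may have formed on drug.

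**The affected subjects appear elsewhere.** A subject positive only at the last time point is classed as indeterminate duration, provided post-baseline sampling spans at least 16 weeks. The same subject counts in overall incidence and, if negative at baseline, as treatment induced. The listing gives days to first positive. All of this stands, and it confines the problem to one descriptive split. None of it corrects that split.

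**Fourteen days matches the exposure rule.** SAP 6.3 computes treatment duration as last dose minus first dose plus 15 days, so treatment runs through day 14. The cut-off is therefore not arbitrary. The difficulty is that it cannot date onset when the previous negative sample may be months old.

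**Some subjects are sampled sooner.** Early-discontinuation visits have no stated 14-day minimum. Protocol 7.2.7.2 adds ADA samples for hypersensitivity reactions and for injection site reactions unresolved by the end of the third day. Both reduce the number affected.

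Three stronger readings are tempting, and the documents do not support them.

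- A reader might infer a conflict with the protocol's safety period: "The safety follow-up period will comprise 40 calendar days after the last administration of the IP". That period governs follow-up and serious adverse event reporting, not attribution of antibodies. SAP 1.1 records that the 40-day safety summaries were deleted. A 40-day cut-off would not cure the problem either, because EOS has no latest day.
- A reader might infer that the four-weekly regimen makes matters materially worse. Protocol 1.2.6 predicts that 0.4% of subjects reach it, about 22 of 5,500 (0.004 × 5,500).
- A reader might take 29% as the share of subjects misfiled. It is a share of dosing time, averaged over an assumed even spread of stop weeks, and it becomes a share of seroconversions only if onset is uniform.

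**Conclusion.** The point holds in limited form. For subjects still taking IP, the definition and the EOS visit rule together make a first positive at EOS off-treatment on every permitted day but one, whenever the antibody formed. That biases the on/off-treatment counts and percentages for ADA and nAb toward off-treatment.

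The conclusion concerns subjects whose first positive is at EOS; anyone with an earlier positive during dosing stays on-treatment. Overall status and incidence, the antibody subgroups and the efficacy tests do not change.

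The number of subjects misfiled cannot be derived, because the documents give neither the distribution of EOS timing nor that of seroconversion times. The supportable bound is on exposure: 0% to about 64% of dosing time is unsampled for stop weeks from Week 14 on. The share of seroconversions affected could be well below that if they are mainly early.

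A related gap is that the SAP does not say whether last dose means the final dose or the most recent one. The analysis above takes it as the final dose.

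**What to change.** Amend the timing definitions in SAP 8.2.4.1.1 as follows, for ADA and nAb alike.

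1. State that last dose means the final dose of study drug.
2. Keep the on-treatment class as defined.
3. Reserve off-treatment for a first positive more than 14 days after the last dose that is preceded by a negative sample also taken after the last dose.
4. Report every other first positive more than 14 days after the last dose in a third class: first detected after last dose, onset on treatment or spanning last dose.
5. Carry the three classes into the tables in SAP 8.2.3 and 8.2.4.2. SAP 8.2.3 points to Section 6.2 for these definitions; correct the reference to 8.2.4.1.1.

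The cost is one definition and a re-run of the timing tabulation from sample and dose dates already collected. No visit, sampling or treatment rule changes. The downside is a third row and few subjects left in the off-treatment row, since a subject who dosed until study end normally has only one sample after the last dose. Those who stopped early and stayed in follow-up are the ones who can still qualify.

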- Blood for fasting lipid profile:

Lipid level tests should be scheduled no sooner than 10 days after the subject's prior dose, even if this requires an unscheduled visit;

If a subject has a visit that is scheduled less than 10 days after the last dose, the visit procedures may take place, but lipid testing should be postponed and performed at the earliest possible time, at an unscheduled visit, no sooner than 10 days after the subject's last dose;

- LFTs;
- Blood specimens acquired for ADA, bococizumab level, and PCSK9 level in all subjects at Visit 6 only;

After randomization, if lipid sampling has been postponed to an unscheduled visit, the corresponding ADA/PK/PCSK9 samples should be postponed as well, and collected at the same time as the rescheduled lipid sample collection;

- Urine and serum for pregnancy testing (if indicated).

#### 6.4.3. Visits 8, 9, 10, 12, 13, 15, 16, 18, and 19

At weeks 14, 26, 40, 70, 86, 122, 140, 174, and 192, the following procedures and assessments should be made before subject self-injection:

- **Laboratory test review:** There should be a review of results from laboratory values of the previous visit.
- **Vital signs:** Temperature, PR, and BP will be measured and recorded in the CRF as described in [Section 7.2.3.1](#).
- **Concomitant medications:** Background prescribed lipid lowering treatment (drug name and dose) and all other concomitant treatments will be recorded in the CRF. Instruct subjects on the use of concomitant medications ([Section 5.8](#)).
- **Health care resource utilization:** Assessment of healthcare resource utilization ([Section 7.7](#))
- **Assessment of AEs (including SAEs) or potential CVD outcome events:** Subjects will be asked if any AEs have occurred. AEs (serious and non serious) should be recorded on the CRF. SAEs should be reported as per the safety requirements of the study ([Section 8.6](#)). Subjects should be specifically interrogated with respect to the occurrence of potential outcome events. Potential CVD outcome events should be reported as required ([Section 8.6.1](#)).
- **EQ-5D:** Subjects will complete brief questionnaire as described in [Section 7.3](#) at Visits 8 and 9 only. Results will be transcribed to the CRF.
- **IRT interaction:** At the time of the visit, the visit will be registered in the IRT which will trigger an allocation of IP for the subject.

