- **Investigational product:** Dispense IP based on IRT randomization code. If there is dosing during the visit, subjects will be observed, at the visit, during the injection of IP, either by self-injection, or as performed by a care giver, after all other procedures have been completed.

Subjects will be provided with IP kits to bring home with them and will be reminded about storage conditions.

- **Compliance check:** The subject's compliance with IP administration, as described in [Section 5.3](#), will be assessed. Collect all used and unused syringe cartons in a biohazards container. Subjects will be instructed to bring any used and unused syringe cartons to each visit. Used syringes will be returned to the study center in a biohazard container, when it is full, to receive a new container, and when directed by the study site, as described in [Section 5.3](#). Compliance with lifestyle guidelines should also be reviewed ([Section 4.4](#)) and recorded in the CRF.

- **Contraception check:** At these visits, a contraception check should be made for male and female subjects, who, with their partner, are of childbearing potential ([Section 4.4.2](#)).

The following laboratory tests should be collected:

- Blood for fasting lipid profile;

Lipid level tests should be scheduled no sooner than 10 days after the subject's prior dose, even if this requires an unscheduled visit;

If a subject has a visit that is scheduled less than 10 days after the last dose, the visit procedures may take place, but lipid testing should be postponed and performed at the earliest possible time, at an unscheduled visit, no sooner than 10 days after the subject's last dose;

- Special lipid and efficacy studies, as described in [Section 7.1.2.2](#), will be collected at Week 14, Visit 8.
- Chemistry group;
- LFTs;
- Blood specimens acquired for ADA, bococizumab level, and PCSK9 level in all subjects at Visits 8, 10, and 12;

After randomization, if lipid sampling has been postponed to an unscheduled visit, the corresponding ADA/PK/PCSK9 tests should be postponed as well, and collected at the same time as the rescheduled lipid sample collection;

- Urine and serum for pregnancy testing (if indicated).

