- **IRT interaction:** At the time of the visit, the visit will be registered in the IRT which will trigger an allocation of IP for the subject, except at the EDC or EOS visit. At the EDC or EOS visit, the EDC or EOS status will be registered.
- **Investigational product:** Dispense IP based on IRT randomization code (except for EDC or EOS visit). If there is dosing during the visit, subjects will be observed, at the visit, during the injection of IP, either by self-injection, or as performed by a care giver, after all other procedures have been completed. Except for EDC or EOS visit, subjects will be provided with IP kits to bring home with them and will be reminded about storage conditions.
- **Compliance check:** The subject's compliance with IP administration, as described in [Section 5.3](#), will be assessed. Subjects will be instructed to bring any used and unused syringe cartons to each visit. Used syringes will be returned to the study center in a biohazard container, when it is full, to receive a new container, and when directed by the study site, as described in [Section 5.3](#). Compliance with lifestyle guidelines should also be reviewed ([Section 4.4](#)) and recorded in the CRF.
- **Contraception check:** At these visits, a contraception check should be made for male and female subjects, who, with their partner, are of childbearing potential ([Section 4.4.2](#)).

The following laboratory tests will be collected:

- Blood for fasting lipid profile;

Lipid level tests should be scheduled no sooner than 10 days after the subject's prior dose, even if this requires an unscheduled visit;

If a subject has a visit that is scheduled less than 10 days after the last dose, the visit procedures may take place, but lipid testing should be postponed and performed at the earliest possible time, at an unscheduled visit, no sooner than 10 days after the subject's last dose;

A lipid profile will not be collected at EDC/EOS visits.

- Special lipid and efficacy studies as described in [Section 7.1.2.2](#), at Month 12, Visit 11;
- Biospecimens as described in [Section 7.5](#), at Week 52, Visit 11;

- Chemistry group (including LFTs and CK level);
- Hematology;
- Urinalysis;
- HbA1c for all subjects at Visit 11 and EDC and/or EOS;
- Blood specimens acquired for ADA, bococizumab level, and PCSK9 level in all subjects at Visits 14, 17, 20, and EDC or EOS;

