8.2.4.3. Summarization of Pharmacokinetics/Pharmacodynamics Results

The following analyses will be performed for plasma bococizumab concentrations, and LDL-C response. The windows from [Table 3](#) in [Appendix 1.1](#) will be used.

1. Listings of all plasma bococizumab concentrations by subject and visit will be provided.
2. Descriptive summaries of observed plasma bococizumab concentrations over time will be provided. Summary statistics will include arithmetic mean, standard deviation, % coefficient of variation, median, minimum, and maximum. The number of concentrations above the lower limit of quantification (NALQ) may also be provided. Observations below the lower limit of quantification will be imputed as zero.
3. Mean (\pm SD) observed bococizumab concentration will be plotted over time.

The following summaries will be provided using only observations meeting the following conditions (without missed doses and prior to dose adjustment):

- Sample collection date minus the previous injection date is between 1 and 21 days.
 - No dose adjustments have occurred prior to sample collection.
1. For plasma bococizumab concentrations, the descriptive summaries, longitudinal mean (\pm SD) plots will be repeated.
 2. For plasma bococizumab concentrations and LDL-C, the descriptive summaries will be repeated by ADA status and by nAb status. For plasma bococizumab concentrations only, box plots by ADA status and nAb status will be presented. For LDL-C, box plots of percent change from baseline will be repeated by ADA status and by nAb status.
 3. For plasma bococizumab concentrations and LDL-C, the descriptive summaries will be repeated by duration of ADA response (indeterminate/persistent/transient) and by duration of nAb response (indeterminate/persistent/transient). For LDL-C, and box plots of percent change from baseline will be repeated by duration of ADA response (indeterminate/persistent/transient) and by duration of nAb response (indeterminate/persistent/transient).

4. For plasma bococizumab concentrations and LDL-C, the descriptive summaries will be repeated by pre-existing ADA status (with pre-existing ADAs, without pre-existing ADAs).
5. For plasma bococizumab concentrations and LDL-C, the descriptive summaries will be repeated by ADA (nAb) titer response (ADA (nAb) negative, ADA (nAb) 1st tertile, ADA (nAb) 2nd tertile, ADA (nAb) 3rd tertile).

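### The residual definition of transient antibody duration can label subjects whose antibodies were never seen to disappear as transient

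*SAP*

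**What the plan says.** SAP 8.2.4.1.1 (Duration of ADA (nAb) Response) gives a positive subject a duration class "if the date of the first post-baseline measurement to the date of the last post-baseline measurement is at least 16 weeks". The classes are:

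- Indeterminate: "The subject has a positive ADA (or nAb) detected at the last post-baseline time point only".
- Persistent: "The subject has positive ADA (or nAb) detected at all post-baseline samples assayed during any period of at least 16 weeks".
- Transient: "The subject has been classified as neither persistent nor indeterminate".

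No minimum number of samples is stated for persistent, and no order of precedence if two classes apply.

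Sampling is set in the Protocol. Section 6.4.2: "Blood specimens acquired for ADA, bococizumab level, and PCSK9 level in all subjects at Visit 6 only" (Week 4). Section 6.4.3: "Blood specimens acquired for ADA, bococizumab level, and PCSK9 level in all subjects at Visits 8, 10, and 12" (Weeks 14, 40, 70). Section 6.4.4: "Blood specimens acquired for ADA, bococizumab level, and PCSK9 level in all subjects at Visits 14, 17, 20, and EDC or EOS" (Weeks 104, 156, 208 and the closing visits). Section 6 gives early-discontinuation (EDC) and end-of-study (EOS) visits no window. Section 7.2.7.2 adds unscheduled samples after hypersensitivity reactions and after injection site reactions unresolved by the end of the third day.

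The class is used in the incidence summary and subject listing (SAP 8.2.4.2), and in the bococizumab concentration and LDL-C summaries and LDL-C box plots (SAP 5.4.2.4 and 8.2.4.3).

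**The concern.** A reader of these tables will take transient to mean that antibodies appeared and then went away. The rule does not require that. A subject who seroconverts shortly before the final sample, and is positive on every sample from then on, has an unknown duration. Indeterminate would describe that, but the class is limited to a positive at the last time point only, so a second positive pushes the subject into the residual class.

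At stake is what the duration tables mean. They would count some subjects as having lost antibodies when no loss was seen, and would show LDL-C and drug concentration by classes that mix late converters with true reverters. Two programmers could also read persistent differently and produce different tables from the same data.

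**Working it through.** The documents state no figure for this rule, so there is none to reproduce. The check applies the rule to the protocol's sampling schedule.

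**1. Schedule.** Post-baseline ADA samples fall at Weeks 4, 14, 40, 70, 104, 156 and 208, with gaps of 10, 26, 30, 34, 52 and 52 weeks, plus EDC/EOS at any time.

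**2. Natural reading of persistent** (an unbroken run of positives spanning at least 16 weeks). Let F be the first post-baseline sample, f the first positive and L the last sample, with no negative after f. The subject is classified if L − F ≥ 16; indeterminate if f = L; persistent if L − f ≥ 16. Otherwise the subject is transient. So a never-reverting subject is called transient exactly when L − F ≥ 16 and 0 < L − f < 16.

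| Samples (week, result) | L − F | L − f | Class |
|---|---|---|---|
| 4−, 14+, EDC 24+ | 20 | 10 | transient |
| 4−, 14−, 40+, EOS 48+ | 44 | 8 | transient |
| 4−, 14−, 40−, 70+, EOS 80+ | 76 | 10 | transient |

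**3. Scheduled visits only.** The only gap under 16 weeks is Weeks 4 to 14, and a subject with only those two samples fails the 16-week eligibility condition. Enumerating all patterns, 0 of 5 never-reverting patterns to Week 104 and 0 of 7 to Week 208 become transient.

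**4. When EDC/EOS triggers it.** With the first positive at Week 14, a closing sample from Week 20 to before Week 30; at Week 40, before Week 56; at Week 70, before Week 86; at Week 104, before Week 120. If EOS times were uniform (an assumption), the share falling in those ranges is (10 + 16)/50 = 52% for Weeks 20–70, and (10 + 16 + 16)/84 = 50% for Weeks 20–104. This is not the share of subjects affected: the last scheduled sample must also be the subject's first positive.

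**5. Share of subjects.** The documents give no sample dates and no time course of seroconversion; Protocol 1.2.3 reports 42.5% (201/473) ADA-positive in earlier studies without timing. The share was therefore simulated with no reversion, accrual over 2.5 years with half in the last six months (Protocol 9.1), and every subject sampled at the program stop. With a stop 3.0 years after first randomization and onset at a median of 14 or 26 weeks, or uniform over Weeks 4–52, about 13–19% of classified positives are labelled transient. Adding median onsets of 4 to 8 weeks and stops at 2.75 to 3.2 years widens this to about 3–19%. Early onset gives the low end and uniform onset the high end; one run of the uniform case gave 20%.

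**6. Literal reading of persistent** (any period of at least 16 weeks containing a positive and no negative). A lone positive at Week 40 between negatives at Weeks 14 and 70 qualifies, because it is the only sample in a period longer than 16 weeks. Of the 31 patterns to Week 104 with at least one positive:

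| Reading | Persistent | Transient | Indeterminate | Both indeterminate and persistent |
|---|---|---|---|---|
| Natural | 16 | 14 | 1 | 0 |
| Literal | 29 | 1 | 0 | 1 |

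No schedule examined gave both errors under one reading: the natural reading never made a lone positive persistent, and the literal reading never made a never-reverting subject transient.

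**The case against.** The strongest reply is that this is loose wording with a confined effect. Several parts of it stand.

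- A reader might infer that both mislabels occur together. They do not. A program implements one reading, and each error belongs to a different one. The literal reading is also implausible as the intent, since it leaves almost nothing in transient.
- A reader might infer that never-reverting subjects in general are called transient. Under the natural reading most are correctly persistent or indeterminate. Only those with at least two positives, the first less than 16 weeks before the last sample, are affected.
- A reader might infer that the LDL-C contrast between persistent and transient is pulled toward zero. Nothing in the documents supports a direction. The affected subjects were negative at all earlier samples, so their earlier LDL-C values may look unaffected by antibodies, and including them in transient could even widen the contrast at early visits. No lipid profile is drawn at EDC/EOS, so the closing sample that creates the mislabel brings no LDL-C value with it.
- The antibody question is also addressed without this label, by ADA status, nAb status and titer tertile (SAP 8.2.4.3). Listings of titer and status allow subjects to be reclassified.

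What the reply does not remove is that, under the more sensible reading, the stated rule puts an identifiable kind of subject in a class whose name contradicts the data.

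**Conclusion.** The point holds in a limited form. Under the natural reading of persistent, the residual definition can label as transient a subject with at least two positives, no later negative, and a first positive less than 16 weeks before the last sample. This requires an EDC/EOS or unscheduled sample soon after conversion. Stopping the program on 01 November 2016 makes that more likely, because closing samples then cut across the visit schedule.

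The number affected is unknown. The 3–19% range rests entirely on the assumed stop time, onset distribution and absence of reversion; that every transient label in the simulation is wrong follows from the last of these. Separately, the missing minimum sample count and precedence leave room for the literal reading and its different error.

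Severity is minor. The incidence summary and the concentration and LDL-C displays by duration are descriptive. The primary and key secondary analyses and the summaries by ADA or nAb status do not use the class.

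**What to change.** Replace the three definitions in SAP 8.2.4.1.1, keeping the 16-week eligibility condition and applying the same rule to nAb:

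- Persistent: at least two consecutive positive samples, the first and last at least 16 weeks apart, with no negative between.
- Indeterminate: not persistent, and the last assayed sample is positive.
- Transient: not persistent, at least one positive, and the last assayed sample is negative.

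The classes are mutually exclusive and exhaustive, so no precedence rule is needed. For samples at Weeks 4, 14, 40 and EOS 48, the 15 patterns with a positive split persistent/indeterminate/transient as 4/1/10 under the natural reading, 12/1/2 under the literal reading and 4/6/5 after the change. These are pattern counts, not subject counts. Relative to the natural reading the persistent class is unchanged. The five patterns moving to indeterminate are the never-reverting one and four that turned negative and were positive again at the last sample, where the final duration is equally unknown.

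The cost is a few lines of SAP text and one derivation, before unblinding, with no new data.
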